**2) Author of Protocol**

- UC Davis Researcher
- Researcher from other institution
- Private Sponsor
- Cooperative Group
- Other: \_\_\_\_\_

**3) IRB Review History**

*n/a.*

**4) Objectives**

**1.1 Primary Objective**

The primary objective of this study is to evaluate whether abatacept is effective in inducing a biochemical response in PBC patients with an incomplete response to UDCA.

**1.2 Secondary Objectives**

The secondary objectives of this study are:

- To assess the safety of abatacept in patients with PBC
- To assess effect of abatacept on liver stiffness as a measure of liver fibrosis in patients with PBC
- To determine the effects of abatacept on immunologic markers of PBC
- To assess the impact of abatacept on the quality of life in patients with PBC
- To characterize pharmacokinetics (PK) of abatacept 125mg administrated SC weekly in patients with PBC
- To assess immunogenicity of abatacept 125mg administered SC weekly in patients with PBC

PROTOCOL TITLE: ABATACEPT FOR THE TREATMENT OF PRIMARY  
BILIARY CIRRHOSIS WITH AN INCOMPLETE BIOCHEMICAL RESPONSE TO  
URSODEOXYCHOLIC ACID

**5) Background**

**Introduction**

Primary biliary cirrhosis (PBC) is a progressive autoimmune disease of biliary epithelial cells resulting in biliary cirrhosis. The prevalence of PBC in the US and Europe is estimated to be 5-40 per 100,000 persons and accounts for 3-4 % of liver transplants performed in the US. The only approved medical therapy of PBC is the hydrophilic bile acid ursodeoxycholic acid (UDCA). Multiple studies suggest that UDCA delays progression of the disease, particularly those that have a biochemical response which has defined by multiple criteria, the simplest being a decrease of the alkaline phosphatase to 1.67 times the upper limit of normal. However, 20-40% of PBC patients have an incomplete response to UDCA and remain at significant risk of disease progression leading to death or liver transplantation.

PBC is characterized by a 90% female predominance, high titers of serum anti-mitochondrial autoantibodies (AMA) directed against the pyruvate dehydrogenase complex E2 subunit and elevated plasma levels of immunoglobulin M (IgM). However, evidence from both human and murine models suggests that T-cells, particularly CD8+ T cells, are key to the destruction of bile ducts. Genetic evidence of a T-cell defect is also supported by our findings and those of others demonstrating significant associations between CTLA-4 polymorphisms and PBC. Most notable, are the results we recently published in our murine model of PBC in which both AMA and biliary inflammation are induced by immunization with the xenobiotic 2-octynoic acid (2-OA). CTLA-4 Ig treatment one day before 2-OA immunization, completely inhibited AMA production, intra-hepatic T cell infiltrates, and bile duct damage. More critically, treatment with CTLA-4 Ig initiated after the 2-OA immunization and development of disease, also resulted in reduced intra-hepatic T cell infiltrates and biliary cell damage, although AMA levels were not altered.

**a) Pathology of Primary Biliary Cirrhosis**

Three important observations must be taken into account for us to understand the pathogenic basis of PBC. First, appearance of AMAs before liver disease suggests that loss of tolerance to the mitochondrial autoantigen is an early event and could be independent of the development of liver disease. Second, although the autoantigen is present ubiquitously in all nucleated cells, the immune response is restricted to epithelial cells of intrahepatic bile ducts and, to a lesser degree, to cells of salivary and lacrimal glands. Finally, recurrence of PBC after liver transplantation supports the idea that the bile duct epithelial cell is a generic target and is not unique to the patient with PBC. Similar to other complex diseases, the combination of a susceptible genetic background and exposure to environmental triggers are needed to initiate and promote the disorder.

PROTOCOL TITLE: ABATACEPT FOR THE TREATMENT OF PRIMARY  
BILIARY CIRRHOsis WITH AN INCOMPLETE BIOCHEMICAL RESPONSE TO  
URSODEOXYCHOLIC ACID

Observations that 1–6% of individuals with PBC have at least one family member manifesting disease and a 63% concordance rate in monozygotic twins (vs null concordance in dizygotic sets), show the substantial genetic effect on disease susceptibility, one of the strongest for any autoimmune disorder. Many candidate genes have been investigated for a role in susceptibility to PBC, disease progression, or both in case-control cross-sectional studies. Findings of a genome-wide association study undertaken in a northern American set of patients and controls indicated a significant association between PBC and polymorphisms of *HLA-DQB1*, *IL12A*, *IL12RB2*, and to a minor extent, *STAT4*, and these associations have been confirmed in an independent cohort of Italian patients and controls with a combined analysis.

Several environmental factors—mainly infectious and chemical—are also thought to contribute to the onset of PBC, largely through molecular mimicry or modification of autoantigens. Geographic clustering of cases near toxic waste sites in New York City and space-time clustering in northeast England provide epidemiological evidence for a role of chemicals, infectious agents, or both. Additional data that lend support to a role for infections in disease development include the significantly higher prevalence than usual of recurrent urinary-tract infections in patients with PBC and experimental findings of sequence similarity between the E2 enzyme of the pyruvate dehydrogenase complex recognized by autoantibodies and bacterial proteins. Several bacterial strains—including the non-pathogenic gram-negative bacterium *Novosphingobium aromaticivorans*—have the highest known homology to the immunodominant autoepitope of the E2 enzyme. Several other infectious agents have been proposed, including *Escherichia coli*, *Helicobacter* spp, organisms of the genus *Mycoplasma*, and a human  $\beta$  retrovirus, although support for the retrovirus has not been substantiated.

Other environmental factors proposed to trigger disease onset are foreign chemicals (ie, xenobiotics) that can either alter or form a complex with a defined self or non-self protein, causing a change in the protein's molecular structure that induces an immune response. Lipoic acid is attached to only a few proteins, yet it is a vital component of the E2 epitope. The structure of the E2 enzyme exposes lipoic acid at the exterior of the protein complex, making this compound accessible to chemical modification. The role of xenobiotics in PBC is supported by serum reactivity against specific organic compounds with structures similar to lipoic acid; furthermore, two of these compounds (6-bromohexanoate and 2-octynoic acid) can induce AMAs and liver lesions similar to those of PBC in guinea pigs and mouse models.

AMAs in serum are highly sensitive and specific for PBC: they are detected in nearly 95% of patients, with specificity close to 100% when tested with recombinant antigens. Indirect immunofluorescence remains the test used for screening, but it can be associated with a substantial number of false-positive results. Follow-up data from AMA-positive individuals without signs of liver disease suggest that autoantibodies arise several years before onset of PBC and have a high predictive value. Epitopes recognized by AMAs

PROTOCOL TITLE: ABATACEPT FOR THE TREATMENT OF PRIMARY BILIARY CIRRHOSIS WITH AN INCOMPLETE BIOCHEMICAL RESPONSE TO URSODEOXYCHOLIC ACID

include lipoylated domains (via the Asx-Lys-Ala motif) within subunits of the 2-oxoacid dehydrogenase family of enzymes of the mitochondrial respiratory chain, in particular, E2 subunit and E3 binding-protein components of the pyruvate dehydrogenase complex and E2 components of the 2-oxoglutarate dehydrogenase and branched-chain 2-oxo acid dehydrogenase complexes.

**b) Role of T cells in Primary Biliary Cirrhosis**

In addition to AMAs, autoreactive CD8+ and CD4+ T cells to the E2 component of the pyruvate dehydrogenase complex have been identified both in peripheral blood and within the liver of patients with PBC, and the immunodominant epitope of these T cells maps in close proximity to the epitope recognized by AMAs in serum. Autoreactive CD4+ cell clones specific for the E2 enzyme have been isolated in intrahepatic and peripheral lymphocytes, not only in AMA-positive individuals but also in patients without antibodies, thus corroborating the notion that PBC either positive or negative for AMAs is one nosological entity.

CD4+ CD25high regulatory T cells act to prevent autoreactivity, as shown in several autoimmune diseases, including autoimmune hepatitis. Patients with PBC are characterized by substantially lower frequencies of CD4+ CD25high regulatory T cells as proportions of total T-cell receptor- $\alpha\beta$ +/CD4+ cells, and this factor could be important in the breakdown of tolerance.

**c) Summary of Results of Investigational Program**

***Pharmacology of Abatacept***

Abatacept is a recombinant fusion protein consisting of the extracellular domain of human CTLA4 and a fragment (hinge- CH2-CH3 domains) of the Fc domain of human IgG1 that has been modified to prevent complement fixation and antibody-dependent cellular cytotoxicity.

Abatacept is the first drug in a new class of agents termed “selective costimulation modulators.” Abatacept binds specifically to the CD80 and CD86 molecules, proteins prominently displayed on the surface of antigen-presenting cells (APCs). Activation of naive T cells during an immune response requires two stimuli from APCs. The first signal is antigen-specific; antigens are presented by APCs, with the signal transmitted to the T cell through the T cell’s antigen receptor. The second, or costimulatory, signal is not antigen-specific and is delivered following the engagement of a costimulatory ligand on the APC with a cognate receptor on the T cell.

A key costimulatory receptor on T cells is CD28. CD28 is constitutively expressed on resting T cells and binds to both CD80 (B7-1) and CD86 (B7-2) on the APC. A

PROTOCOL TITLE: ABATACEPT FOR THE TREATMENT OF PRIMARY BILIARY CIRRHOsis WITH AN INCOMPLETE BIOCHEMICAL RESPONSE TO URSOODEOXYCHOLIC ACID

costimulatory signal is required not only for the full activation of naive T cells, but also may be required for the survival of memory and autoimmune effector cells. At 24 to 48 hours following T cell activation, the T cell expresses CTLA4 on its surface, which engages the CD80 and CD86 molecules on the APC surface interfering with CD28's ability to bind to its ligands on the APC; CD80 and CD86 preferentially bind to CTLA4 with a much higher avidity than with CD28. Although the precise mechanisms are as yet unclear, CTLA4 expression is associated with a decrease in T cell activation.

After the T cell activity has been damped, the CTLA4 recycles into the T cell's cytoplasm. The CTLA4 section of abatacept binds specifically to CD80 and CD86 (B7-1 and B7-2, respectively) and down-modulates the CD28-mediated costimulation of T cells. Thus, abatacept uses a segment of a molecule that is part of the normal immune homeostatic mechanism to suppress T cell activity involved in the immunopathogenesis of autoimmune diseases. The FC region of abatacept was engineered with several point mutations designed to inactivate it. Because of these changes, abatacept does not mediate pathways such as antibody-dependent cell cytotoxicity or complement-dependent cytotoxicity.

### **Study Rationale**

This is an open label, single center, active treatment study of the effects of abatacept on PBC patients with an incomplete response to UDCA. These patients have been demonstrated to have increased morbidity and mortality with standard-of-care treatment. An abundance of human and pre-clinical data suggests that T cell activation is central to the immune-mediated destruction of biliary epithelial cells and that abatacept may be effective in halting this process.

## **6) Inclusion and Exclusion Criteria**

### ***Inclusion Criteria***

#### **1. Signed Written Informed Consent**

- a) Before any study procedures are performed, subjects will have the details of the study described to them, and they will be given a written informed consent document to read. Then, if subjects consent to participate in the study, they will indicate that consent by signing and dating the informed consent document in the presence of study personnel.

#### **2. Target Population**

- a) Confirmed PBC diagnosis based upon at least 2 of 3 criteria
  - i) AMA titer > 1:40
  - ii) Alkaline phosphatase > 1.5 times the upper limit of normal for at least 6 months
  - iii) Liver biopsy findings consistent with PBC

PROTOCOL TITLE: ABATACEPT FOR THE TREATMENT OF PRIMARY  
BILIARY CIRRHOSIS WITH AN INCOMPLETE BIOCHEMICAL RESPONSE TO  
URSODEOXYCHOLIC ACID

- b) Incomplete response to UDCA defined by an alkaline phosphatase  $> 1.67$  times the upper limit of normal after 6 months of UDCA at a minimum dose of 13 mg/kg/d.
- c) Taking a stable dose of UDCA for at least 3 months prior to Day 0.
- d) Willing and able to comply with all study requirements.
- e) AST and ALT  $\leq 5$  X the upper limit of normal

**3. Age and Reproductive Status**

- a) Men and women, 18 to 80 years of age.
- b) **Reproductive Status: Definition of Women of Child-Bearing Potential (WOCBP).** WOCBP comprises women who have experienced menarche and who have not undergone successful surgical sterilization (hysterectomy, bilateral tubal ligation, or bilateral oophorectomy) or who are not post-menopausal (see definition below).
  - 1) Post-menopause is defined as:
    - Women who have had amenorrhea for  $\geq 12$  consecutive months (without another cause) and who have a documented serum follicle-stimulating hormone (FSH) level  $> 35$  mIU/mL.
    - Women who have irregular menstrual periods and a documented serum FSH level  $> 35$  mIU/mL.
    - Women who are taking hormone replacement therapy (HRT).

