**The following women are WOCBP:**

- Women using the following methods to prevent pregnancy: Oral contraceptives, other hormonal contraceptives (vaginal products, skin patches, or implanted or injectable products), or mechanical products such as intrauterine devices or barrier methods (diaphragm, condoms, spermicides).
- Women who are practicing abstinence.
- Women who have a partner who is sterile (eg, due to vasectomy).
- WOCBP must be using an acceptable method of contraception to avoid pregnancy throughout the study and for up to 10 weeks after the last dose of study drug in such a manner that the risk of pregnancy is minimized.
- WOCBP must have a negative serum or urine pregnancy test result (minimum sensitivity 25 IU/L or equivalent units of HCG) within 0 to 48 hours before the first dose of study drug.
- Women must not be breast-feeding.
- Sexually active fertile men must use effective birth control if their partners are WOCBP.

PROTOCOL TITLE: ABATACEPT FOR THE TREATMENT OF PRIMARY  
BILIARY CIRRHOsis WITH AN INCOMPLETE BIOCHEMICAL RESPONSE TO  
URSODEOXYCHOLIC ACID

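### The definition of child-bearing potential fails on either reading of its *or*: literally, its post-menopause clause releases no unsterilized woman; as probably intended, two of three routes lift the contraception rule without 12 months of amenorrhea

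*Combined protocol and SAP*

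**What the plan says.** All of the wording at issue is in the combined protocol and SAP, section 6, Inclusion Criteria, item 3.

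- **The definition.** WOCBP are women past menarche who are not surgically sterilized "or who are not post-menopausal (see definition below".
- **Post-menopause, route 1.** Amenorrhea for at least 12 "consecutive months (without another cause) and who have a documented serum follicle-stimulating hormone (FSH) level" above 35 mIU/mL.
- **Post-menopause, route 2.** "Women who have irregular menstrual periods and a documented serum FSH level" above 35 mIU/mL.
- **Post-menopause, route 3.** "Women who are taking hormone replacement therapy (HRT"), with no further condition.
- **The rule that depends on it.** "WOCBP must be using an acceptable method of contraception to avoid pregnancy throughout the study and for up to 10 weeks" after the last dose.
- **A list of women declared to be WOCBP.** It names "Women using the following methods to prevent pregnancy: Oral contraceptives, other hormonal contraceptives" and mechanical or barrier methods; "Women who are practicing abstinence"; and "Women who have a partner who is sterile (eg, due to vasectomy"). HRT users and women with irregular periods are not on it.

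Section 16 (Withdrawal of Subjects) addresses the instruction to report a suspected pregnancy immediately to WOCBP. It makes pregnancy a mandatory reason to stop study drug for any subject. The Time and Events Schedule in section 12 has a urine pregnancy test (UPT) row marked at pre-treatment, Day 1 and Weeks 4, 12 and 24.

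**The concern.** The definition decides who must use contraception while on abatacept and for up to 10 weeks afterwards. Route 1 treats a raised FSH as insufficient without a year of amenorrhea. Route 2 drops the amenorrhea for women who still have periods, and route 3 drops both conditions. If these routes release women from WOCBP status, a woman who may still be fertile could take the drug with no contraception requirement. If they do not, because of the *or*, the protocol spells out a post-menopause definition that changes nothing for the women it describes. Staff then cannot tell which rule to apply.

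**Working it through.** There is no stated figure to reproduce. The check is of logic, followed by one sum.

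**Step 1: the conjunction.** Take a woman past menarche. *Literal* means not sterilized OR not post-menopausal. *Intended* means not sterilized AND not post-menopausal.

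| Sterilized | Post-menopausal | Literal *or* | Intended *and* |
|---|---|---|---|
| No | No | WOCBP | WOCBP |
| No | Yes | WOCBP | released |
| Yes | No | WOCBP | released |
| Yes | Yes | released | released |

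The literal column is the same whether menarche is grouped with sterilization alone or with both conditions. On the literal text an unsterilized woman is always WOCBP, and so is a sterilized pre-menopausal woman.

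**Step 2: the routes, on the *and* reading.** Take an unsterilized woman past menarche and cross four yes/no facts: 12 months of amenorrhea, irregular periods, FSH above 35, HRT. Amenorrhea and irregular periods exclude each other, which leaves 12 combinations, 8 of them without the 12 months of amenorrhea. Of those 8, 5 are classed as post-menopausal:

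- 4 through HRT use, whatever the periods or FSH;
- 1 through irregular periods with FSH above 35 and no HRT.

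These are logical combinations, not proportions of patients.

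**Step 3: what lapses for a released woman.** The contraception rule and the report-at-once instruction are both written for WOCBP only. Counted from the first dose, the contraception rule runs 24 + 10 = 34 weeks if the last dose is at Week 24. It runs 23 + 10 = 33 weeks if the last weekly dose is at Week 23, and 36 weeks if the study is taken to include the Week 36 visit.

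**Step 4: the list of women declared WOCBP.** If the list overrides the definition, it brings back women who use a listed method, are abstinent or have a sterile partner. The gap is then limited to route 2 or route 3 women in none of those groups. If it does not override, all route 2 and route 3 women are released.

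**Step 5: number affected.** Section 7 caps enrolment at 20. The documents give no distribution of menopausal status or HRT use, so the number cannot be computed.

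**The case against.** The strongest reply is that the text as written contains no safety gap. It says *or*, and on that wording the contraception rule binds every unsterilized woman after menarche. The gap opens only if *and* is substituted, and the documents do not say that *and* was meant. This stands as a limit on the claim. A reader might infer that the protocol, as worded, leaves fertile women without contraception; the literal text does not. The *and* reading remains the probable one, because otherwise the post-menopause definition has no function for unsterilized women.

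Second, the documents do not show that these women can conceive, and route 2 keeps the FSH threshold. That also stands: continuing fertility is an assumption. The inconsistency with route 1 does not depend on it.

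Third, a reader might take the widening intervals between pregnancy tests, or the lack of a scheduled test after Week 24, as a consequence of this defect. They are not. The same schedule applies to WOCBP, and rewording the definition would not alter it.

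Fourth, a reader might infer either that released women keep all the scheduled tests or that they lose them. Neither is secure. The footnote mark on the UPT row points to a note about subjects who discontinue, which fits the Week 36 column carrying the same mark. The UPT mark therefore looks misnumbered, and whether the row is limited to WOCBP is uncertain. Section 16 also leaves the frequency of on-study tests for WOCBP to institutional policy and local regulations.

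Finally, the text between sections 16 and 19, and some text after the schedule, was not available. Other pregnancy precautions may be there.

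**Conclusion.** The definition is wrong as written and should be corrected. On the literal *or* it is over-inclusive, and the post-menopause clause releases no unsterilized woman. On the probable *and*, two of the three routes lift the contraception rule and the report-at-once instruction without 12 months of amenorrhea, contrary to route 1. These are alternative defects; they do not both apply at once.

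The size is modest: an unknown and probably small number of women among at most 20 subjects, smaller still if the list of declared WOCBP takes precedence. Pregnancy remains a mandatory stop for anyone. The point concerns a patient-safety rule only; no endpoint, sample size or analysis changes. It rests on two assumptions: that *and* was intended, and that a woman who still has periods, or who takes HRT without earlier amenorrhea, may be fertile.

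**What to change.** Make three edits together:

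1. Change *or* to *and*, so that WOCBP are women past menarche who are not surgically sterilized and not post-menopausal.
2. Delete route 2, so that women with irregular periods remain WOCBP.
3. Limit route 3 to HRT users who had at least 12 consecutive months of amenorrhea, without another cause, before HRT began. Treat other HRT users as WOCBP.

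Route 1 stays as it is. Edit 1 must not be made alone, because it would turn over-inclusive text into the gap. With all three, none of the 5 combinations in step 2 is released unless the woman is on HRT and had the required amenorrhea before starting it.

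Edit 3 deliberately does not ask for a pre-HRT FSH on record. Requiring one would put long post-menopausal HRT users under mandatory contraception for want of an old laboratory result, in a trial that enrols to age 80. The price is that route 3 is slightly looser than route 1.

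The cost is one conjunction, one deletion and one qualifier, plus taking a menstrual history from HRT users. A few more women would need contraception counselling, and possibly pregnancy tests if the UPT row proves to be limited to WOCBP.

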**The following women are WOCBP:**

- Women using the following methods to prevent pregnancy: Oral contraceptives, other hormonal contraceptives (vaginal products, skin patches, or implanted or injectable products), or mechanical products such as intrauterine devices or barrier methods (diaphragm, condoms, spermicides).
- Women who are practicing abstinence.
- Women who have a partner who is sterile (eg, due to vasectomy).
- WOCBP must be using an acceptable method of contraception to avoid pregnancy throughout the study and for up to 10 weeks after the last dose of study drug in such a manner that the risk of pregnancy is minimized.
- WOCBP must have a negative serum or urine pregnancy test result (minimum sensitivity 25 IU/L or equivalent units of HCG) within 0 to 48 hours before the first dose of study drug.
- Women must not be breast-feeding.
- Sexually active fertile men must use effective birth control if their partners are WOCBP.

PROTOCOL TITLE: ABATACEPT FOR THE TREATMENT OF PRIMARY  
BILIARY CIRRHOsis WITH AN INCOMPLETE BIOCHEMICAL RESPONSE TO  
URSODEOXYCHOLIC ACID

